PROSPECTIVE STUDY OF MEDICAL THERAPY AGAINST CRYOBALLOON ABLATION IN PATIENTS WITH SYMPTOMATIC RECENT ONSET PERSISTENT ATRIAL FIBRILLATION:
METACSA

[name], [name], [name], TBD, [name] and [name]

BACKGROUND

Atrial fibrillation (AF) is the most common cardiac arrhythmia and causes significant morbidity and mortality. AF is not benign, as the mortality risk is doubled and the risk for stroke, left ventricular dysfunction and hospitalization are increased. The prevalence is 1-2%, and increases with age. [1] The health care burden is substantial. [2]

Treatment of AF is targeted on prevention of thrombo-embolic complications and the reduction of symptoms. Medication includes anticoagulation and anti-arrhythmic drugs (AAD) for either rhythm or rate-control. Although AAD are the first line of therapy, they have their shortcomings, as most AAD have been shown only to be 40-50% effective in maintaining sinus rhythm and may have serious side effects. Only amiodarone performs better, but its side effects are substantial, and it is withdrawn of treatment in about 20% of patients, which makes its efficacy comparable to that of propafenone. [3,4]

Ablation of the pulmonary veins (pulmonary vein isolation, further PVI) has proven to be a safe and effective treatment for AF with variable success rate, depending on the AF type, and the presence or absence of underlying disease. [5,6] Recent data show that non-repeated PVI with radiofrequency (RF) ablation, has only a limited effect at one year (50-60%). These results can be improved with a repeated ablation, and seem not

be maintained after 5 year. [7-11] These are some of the arguments that alternative techniques are still being investigated, inclusive minimal invasive surgical techniques.

Success rates, at least similar to RF ablation have been reported after 1-year follow-up and later with a freedom from AF of 69-77% in patients using a cryoballoon technology (CBA). [12-14]. CBA seems to be a reproducible technique, with the same outcome in different centers. It has theoretically less side effects than RF, and its only specific side effect is phrenic nerve paresis.

Results are better in paroxysmal patients, than for persistent AF, also for CBA. [13] Nevertheless, persistent patients with normal left atrial dimensions made up an important proportion of our group. [15] Differentiation between paroxysmal and short term persistent becomes almost impossible from a clinical point of view, as patients get early cardioversion, before they are spontaneously reverted to sinus rhythm. [16] Real longstanding persistent patients, however were excluded from our and all previous trials, as were patients with very large atria. Larger atria have more recurrences than smaller atria. Successful ablation results in a smaller left atrial volume, which was shown in several studies with RF, also for paroxysmal patients. [17] This volume reduction is antiarrhythmic as well.

It has been hypothesized that early therapy prevents further progression of the disease. [16] This has never been proven for catheter ablation, while some pilot trials were promising. [18] Reduction of left atrial volume can be used as a substitute for antiarrhythmic efficacy and for less disease progression.

RATIONALE

Limited data indicate that ablation is better than AAD therapy. The 9 small randomized clinical trials as recently summarized by health care authorities with a correct methodology only included 971 patients, and only studied radiofrequency ablation. [19] However, there was substantial heterogeneity, with a majority of paroxysmal patients, but some had mixed groups. Endpoints in these trials were not always clear and variable as well. Side effects of ablation were somewhat neglected. Stop-AF only addressed paroxysmal patients (but included 22% cardioverted patients) and has recently been published. [14] This opens the perspective to organize a prospective trial comparing the efficacy and safety of CBA to standardized medication for treatment of paroxysmal AF and early onset persistent AF without structural heart disease. As elsewhere a trial is launched for first onset paroxysmal AF, we would like to focus in this protocol *on early onset persistent AF without structural heart disease*. The value of CBA in these patients has never been studied; the endpoints for persistent patients are much easier than for paroxysmal patients. Reduction in LA size can be compared versus patients on drug therapy and versus failing patients.

HYPOTHESIS

1. The results of CBA in early onset persistent AF are better compared to standard medical therapy with as endpoint maintenance of sinus rhythm after 1 year and an improved QOL in the ablation group.
2. Successful CBA results in reduction of the LA volume.

INCLUSION/EXCLUSION CRITERIA

The total AF history is regarded for previous episodes, paroxysmal or persistent. ~~should be shorter than 24 months~~. Symptomatic patients can be included if they have had at

least 2 episodes in their total history, of which one within the last year. One episode in the entire history should have lasted more than 7 days **48 h**, requiring electrical or pharmacological cardioversion or stopped spontaneously after more than 7 days. The duration of this episode should be shorter than 1 year. If one episode is paroxysmal it should have been lasting minimal 30 sec.

All patients eligible for the study will sign informed consent, have an echocardiogram prior to inclusion to exclude severe left ventricular dysfunction, to rule out significant valve abnormalities, left ventricular hypertrophy and to assess the left atrial (LA) volume and diameter.

Prior to randomization, and after inclusion it is suggested to the local investigators to perform an MRI-scan or CT scan of the LA and pulmonary veins (in both branches of the study) in eligible patients to assess the anatomy and the left atrial volume. The results should not influence the strategy of treatment.

Inclusion criteria

- > 21 years and legally capable
- history of 2 symptomatic AF episodes more than 30 sec .
- At least one AF episode within the last year
- One episode cardioverted after more than 7 days or spontaneously terminated after more than 7 days; this episode should have been shorter than one year
- Eligible for at least one first step drug therapy (sotalol, propafenone, or flecainide) **and/or** for amiodarone

- Left ventricular ejection fraction estimated > 45%
- LA diameter < 50 mm (parasternal short axis) **and/or** LA volume less than 100 ml (apical view, Area Length method)
- No previous CVA or TIA (the latter with documented deficit on CT scan)
- ~~CHADS2VASC ≤ XXXX~~
- Failed AAD strategy, or untreated with AAD
- No use of Amiodarone in the previous 6 weeks (except IV or oral for 7 days)
- Informed consent

Exclusion criteria

- Age **> = 80** yrs
- CHF
- Ischemic heart disease as known in the history
- (Severe) Left ventricular hypertrophy as shown on echo (IVSd or PWd > 14 mm)
- Uncontrolled Hyperthyroidism
- Congenital heart disease
- HCM, ARVC, channelopathies
- Contra-indications to AAD
- Long QT syndrome

- Received already adequately dosed all level 1 drugs (sotalol, propafenone, and flecainide) and >6 weeks amiodarone
- Pure (typical) atrial flutter as documented on one occasion

INVESTIGATION DESIGN

Type

Randomized study design. Experienced centres/operators with a load of > 50 cryoablations/year.

Randomization

1:1 at the time of inclusion

SAMPLE SIZE

The maximal expected 1 year success on AAD is 50% and minimal expected success of CBA is 72%. [3,14,15,20,21,22] With a power of 0.8 and a significance of 0,05, approximately 76 patients should be included in each arm. A total number of 167 patients need to be included in the study when anticipating that 10% of the patients will not be followed as required.

INTERVENTIONS

Run-in period (from month -1 till month 0)

Holter recording in the month after inclusion, preferably directly after inclusion to avoid extra visits.

MRI or CT scan to measure LA volume and PV sizes and anatomy is encouraged

(optional – if done it should be done in both branches)

Ablation arm (at month 0):

The ablation approach should be as standardised as possible, and will be discussed at the investigators meeting

After venous punctures, 5000 IE of heparin is administered and after the transseptal puncture (TSP) this is repeated. Hereafter, heparin infusion is started with a target ACT of at least 275-300 s. A multipolar catheter will be introduced into the coronary sinus. Single TSP will be performed (guided by X-ray and intracardiac echocardiography or transoesophageal echocardiography). The 12 Fr steerable sheath is introduced into the LA, and the second generation (large) cryoballoon with the Achieve catheter is introduced. Before ablation is started, the veins are checked for entrance and exit block. If there is conduction a balloon application is given during 300 s. The occlusion grade, maximal freezing temperature and time to isolation are noted. Every vein with potentials is ablated at least twice with at least one grade IV occlusion, except when PNP occurs at the right upper PV. If not isolated, a third application can be given. If after the third application the vein is still not occluded it is up to the physician to decide to do another balloon application or to use a freezer catheter.

If isolated, the veins are checked after 30 minutes again for entrance and exit block. The left sided veins are ablated while pacing from the distal CS electrodes and when ablating the right sided veins the phrenic nerve is stimulated to prevent phrenic nerve palsy (PNP). When all veins are isolated AF induction is preformed, 5 s of pacing with CL 200 ms from the distal CS, LA roof (twice) en the HRA. Procedure times , X-ray times, and the radiation dose (mGy) are noted.

Ablation should be scheduled 4 weeks after cardioversion/inclusion. All patients should

be anticoagulated for at least 4 weeks prior to ablation. Antiarrhythmic drugs are maintained after cardioversion. One day before or the day of ablation a TEE will be made to exclude a LAA thrombus. Anticoagulation can be continued if this is the protocol of the participating centre, and the local protocol per ablation should be followed.

Proposed first level:

A: propafenone 300 mg BID / 150 mg QID if < 70 years and > 70 kg

propafenone 150 mg TID if ≥ 70 years or < 70 kg

B: sotalol 120 mg BID if men ≤ 70 years, cr ≤ 1,5mg/130 µmol, > 70kg;

80 mg TID if men ≥ 70 years, cr > 1,5mg/130 µmol, < 70kg;

if women ≤ 70 years; cr ≤ 1,2/110 µmol

80 mg once if women > 70 years or cr > 1,2 mg/110 µmol

C: Flecainide : Apocard Retard 100 mg/day as startdosis 4 to 5 days

Further 200 mg/day

Tambocor 100 mg BID if preferred

Proposed second level:

Amiodarone: loading 14 days with 600 mg/day

One week 400 mg/day

Maintenance 200 mg/day

Drug arm:

Anticoagulation should be continued per protocol (4 weeks) after the cardioversion. If the CHADS2VASC is \leq 2, anticoagulation is left at the discretion of the physician. A first level antiarrhythmic drug regimen is started at the month -1, time of the inclusion and

an adequate dosage is prescribed. If the patients' condition requires so, a reduced dosage can be used during the first (5-7) days.

If at month 0, at the first clinical visit, the drug therapy does not look sufficient, another

Level 1 treatment can be used. This can be repeated if the clinical condition requests so.

The second slevel antiarrhythmic drug therapy is only allowed after failure of at least one level 1 drug. As this is amiodarone, its final efficacy can only be judged 6 months after its initiation.

FOLLOW UP : see flow charts Is in agreement with proposal in ref 23.

- 24 hour Holter:
 - after inclusion (month -1) and repeated at months 3 .This will be done with the study Holter without necessarily influencing the therapy (so called blanking period)
- 48 hour Holter: with a clinical device
 - at the end of 6 months .
- 7 days Holter: with a clinical device
 - at the end of 12 months .
- Clinical visits :

should be performed by the study nurses/supervised by the investigators

- At months 3, 6, and 12 months after ablation
- Additionally at month 0 for the drug arm, while the ablation group is admitted
- Office ECG ;
 - ° at month 3, 6 and 12
- Drug management:
 - AAD: After 3 months stop AAD in the ablation arm in those patients free of AF episodes.
 - OAC: After 6 months consider stopping oral anticoagulation, or replacing them with antithrombotic medication in patients free of AF episodes if the scores allow so.
- Echocardiogram:
 - At month 12 a new echocardiogram is obtained to assess the LA volume and diameter.
- QOL with disease specific questionnaire (AFQOL 18)
 - At baseline and at month 12
- Blood samples
 - At baseline and at months 6 and 12
 - Thyroid tests (TSH), liver function (AP, SGOT, SGPT), creatinine

- Drug diary
 - At baseline, at month 0 and at months 6 and 12 for all patients in both arms
- Cost calculation: data should be prospectively collected in CRF at the time of scheduled and unscheduled visits, based on costs as foreseen in the reimbursement of the RIZIV/INAMI and additional drug costs.

CROSS OVER

Is allowed after 6 months. This implies that at 12 months we will be able to do not only ITT but also OTA.

SERIOUS ADVERSE EVENTS

SAE's are expected to happen in 7% in the ablation arm, and at a rate of 12-15% in the drug arm, because of side effects and 3% because of proarrhythmia (20).

ENDPOINTS

Primary endpoints

- Sinus rhythm at clinical visit at 1 year after the ablation, or with AAD
- Freedom of AF with all measurements

Secondary endpoints

- Reduction of LA volume in successfully treated patients
- Number of cardioversions
- Percentage of patients on AAD after 6 and 12 months

- Vascular complications
- Stroke, TIA
- SAE in both groups
- Number of cross-overs (with OTA)

[figure not shown]

Figure 1. AAD : antiarrhythmic drugs; LA: left atrial; QOL: quality of life; R: randomization

STUDY ORGANISATION

Steering committee : [name], [name], [name], [name]

DMSB : [name], [name], [name]

One central study coordinator (University Hospital Ghent) – [name]

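### Baseline left atrial volume is planned for every patient and the protocol treats left atrial size as prognostic, but no readable text uses it for adjustment or stratification; pre-specifying it as a covariate is a low-cost gain of modest, uncertain size

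*Protocol*

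**What the plan says.** - **Prognosis.** Protocol, Background: "Larger atria have more recurrences than smaller atria". This states an association and gives no size.
- **Baseline measurement.** Protocol, Inclusion/Exclusion Criteria: all eligible patients have an echocardiogram before inclusion, among other things "to assess the left atrial (LA) volume and diameter". Only the MRI or CT scan is optional. Entry is limited to an LA diameter below 50 mm and/or an LA volume below 100 ml.
- **Randomisation.** Protocol, Randomization: 1:1 at inclusion. No stratification factor is mentioned.
- **Sample size.** Protocol, Sample Size: expected one-year success is 50% on drugs and 72% after cryoballoon ablation. "With a power of 0.8 and a significance of 0,05, approximately 76 patients should be included in each arm". The total is 167, allowing for 10% not followed as required.
- **Analysis.** Protocol, Cross Over, mentions ITT and OTA analyses. No test, model or covariate is named for the primary endpoints, which are binary.
- **LA volume as an outcome.** Protocol, Secondary endpoints: "Reduction of LA volume in successfully treated patients". Echo LA volume is measured again at month 12. The AFQOL 18 questionnaire is given at baseline and month 12.

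The SAP's text was not available to read, so nothing here describes what it does or does not contain.

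**The concern.** The protocol names a prognostic factor, plans to measure it in everyone before treatment, and then, in the readable text, uses it only as an entry limit and an outcome. With about 76 patients per arm and no stratification mentioned, the arms can differ by chance in mean LA volume, and nothing visible deals with that.

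Two things are at stake. One is precision: a covariate that predicts the outcome explains part of its variation, and an analysis that ignores it gives up that part. The sample size leaves no spare power to absorb this. The other is credibility: if LA volume turns out imbalanced, a positive result can be challenged and a narrow miss will be explained away. An adjustment added after the data are seen answers neither convincingly, whereas one fixed in advance does.

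**Working it through.** **1. Reproducing the planned sample size.** Inputs from the Sample Size section: p0 = 0.50, p1 = 0.72, power 0.80, alpha 0.05 (taken as two-sided; sidedness is not stated). With the pooled two-proportion formula and mean rate 0.61:

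n = [1.960 × √(2 × 0.61 × 0.39) + 0.842 × √(0.50 × 0.50 + 0.72 × 0.28)]² / 0.22² = 75.97, so 76 per arm.

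This matches the protocol. The one-sided version gives 60, and the two-sided version with continuity correction gives 85. Nothing in the calculation allows for a covariate. Adding 10% gives 152 × 1.10 = 167.2, the stated 167. Losing 10% of 167 leaves about 75 per arm, with power 79.5%.

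**2. Power with and without adjustment, 76 per arm.** The documents do not say how strongly LA volume predicts failure, so the odds ratio (OR) per SD is an assumption, varied from 1.25 to 3. Marginal success rates are held at 50% and 72%, and LA volume is a standardised normal variable. The asymptotic columns use the variance of the covariate-standardised risk difference; unadjusted power with the same unpooled variance is 81.4%. The simulated columns (4,000 trials per row) compare a pooled z test with a logistic likelihood-ratio test that includes LA volume.

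| Assumed OR per SD | Adjusted power, asymptotic | n per arm for the power of 76 unadjusted | Simulated, unadjusted | Simulated, adjusted |
|---|---|---|---|---|
| 1.0 | 81.4% | 76 | 81.4% | 80.9% |
| 1.25 | 81.9% | 75 | not run | not run |
| 1.5 | 82.8% | 73 | 80.4% | 81.0% |
| 2.0 | 84.9% | 69 | 81.5% | 84.8% |
| 2.5 | 86.9% | 65 | not run | not run |
| 3.0 | 88.5% | 62 | 81.1% | 88.1% |

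The simulation error of each power is about √(0.8 × 0.2 / 4000) = 0.6 points, so the simulated gain at OR 1.5 is no larger than noise. The gain is about 3 points at OR 2 and 7 at OR 3.

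**3. Chance imbalance.** The standard error of the difference in mean LA volume between arms, in SD units, is √(2/76) = 0.162. The probability that the difference exceeds 0.2 SD in either direction is 22%; for 0.3 SD it is 6%. With a 0.3 SD imbalance against ablation, the expected crude difference falls from 22 points to:

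- 19.3 at OR 1.5 (shift 2.7)
- 17.7 at OR 2 (shift 4.3)
- 15.9 at OR 3 (shift 6.1)

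For scale, the smallest significant crude difference at 76 per arm is about 1.96 × √(2 × 0.61 × 0.39 / 76) = 15.5 points. An imbalance in favour of ablation works the other way: 26.2 points at OR 2.

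**4. Continuous outcomes, randomised arms only.** With equal variances σ² at baseline and month 12 and correlation ρ, a change score has variance 2σ²(1 − ρ), and the month-12 value adjusted for baseline has variance σ²(1 − ρ²). The ratio is (1 + ρ)/2: 0.75 at ρ = 0.5 and 0.90 at ρ = 0.8 (assumed values). This requires groups formed by randomisation. The stated LA endpoint concerns successfully treated patients, a group defined by outcome, so the ratio does not apply to it.

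**The case against.** The strongest objection is that no defect has been shown. A reader might infer from the match in step 1 that the primary comparison is planned as an unadjusted test. The documents do not support that: a sample-size formula shows how n was chosen, not how the data will be analysed, and it is compatible with a later adjusted analysis. No test is named in the protocol, and the SAP text could not be read. This stands, and the point is limited accordingly.

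A reader might also infer that an unadjusted result would be biased. It would not. Randomisation keeps the unadjusted comparison valid, type I error is not inflated, and the usual standard error already covers chance imbalance. A 0.3 SD imbalance specifically against ablation has only about a 3% chance, half of the two-sided 6%. This stands too.

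The size rests on assumed odds ratios. The Background sentence is an association, not a claim that LA size drives recurrence, and the entry limits narrow the LA range, which makes the weaker odds ratios more plausible. This stands.

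Finally, the word reduction in the secondary endpoint might be read as a commitment to raw change scores. It names an outcome and leaves the analysis open. A comparison of the randomised arms on LA volume is a different estimand from the endpoint in successfully treated patients.

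What the objection does not remove is that a baseline variable the protocol itself regards as prognostic has no stated role in the readable analysis, and that giving it one in advance needs no new data.

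**Conclusion.** The point holds as a recommendation on efficiency and robustness, not as an error in the plan. The readable text specifies no use of baseline LA volume in the primary comparison or in randomisation, and the sample size assumes none. The sample size itself is correct for its inputs and needs no increase.

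The benefit of adjusting is uncertain. It is close to nil if LA volume is weakly prognostic within the entry limits and substantial only if the odds ratio per SD nears 3; the middle of the range, 1.5 to 2, is worth about 1 to 3 points of power. With no association at all the loss is negligible (80.9% against 81.4% in simulation, within noise). Protection against an awkward imbalance is the other half of the argument: uncommon at 0.3 SD, but large enough at the stronger odds ratios to bring the expected difference close to the significance limit.

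These figures assume a normally distributed LA volume, the protocol's own success rates, complete data on 76 per arm, and odds ratios that are not in the documents. If the SAP already adjusts the primary analysis for baseline LA volume, that part of the point is met.

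**What to change.** Check the SAP first. If it does not already do so, add:

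1. **Primary analysis.** In the ITT population, a logistic model with treatment arm and baseline echo LA volume as a continuous covariate, reported as a standardised (marginal) risk difference with its confidence interval. Give the unadjusted difference as support.
2. **Missing baseline.** A simple rule fixed in advance, because entry is allowed on diameter and/or volume and some patients may lack a recorded volume. No patient should leave the primary analysis for this reason.
3. **Covariate timing.** Use only the pre-inclusion value. Month-12 LA volume is measured after treatment and must not be a covariate.
4. **Month-12 LA volume and AFQOL 18.** Where the randomised arms are compared, analyse the month-12 value adjusted for its own baseline. Present the LA volume comparison between arms as an addition to the stated endpoint in successfully treated patients, not as a replacement for it.
5. **Sample size.** Leave it unchanged.

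The cost is a few sentences in the SAP. No new measurement, visit or patient is needed.

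### Randomisation text does not use prior antiarrhythmic drug status, although the protocol enrols both drug-failed and untreated patients; using it is a minor, nearly free improvement

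*Protocol*

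**What the plan says.** - **Who enters.** The protocol's inclusion criteria accept "Failed AAD strategy, or untreated with AAD". The related exclusion removes only patients at the far end of drug exposure: "Received already adequately dosed all level 1 drugs (sotalol, propafenone, and flecainide) and >6 weeks amiodarone". Patients who failed one or two first-level drugs therefore stay eligible alongside patients never treated.
- **Control treatment.** The drug arm starts on a first-level drug and may switch to another. Second-level "antiarrhythmic drug therapy is only allowed after failure of at least one level 1 drug".
- **Allocation.** The Randomization section reads, in full, "1:1 at the time of inclusion". It names no strata, blocks or minimisation factors.
- **Sample size.** One success rate is given per arm: "The maximal expected 1 year success on AAD is 50% and minimal expected success of CBA is 72" (per cent). Neither rate is split by prior drug status. The result is 76 per arm, or 167 in total after a 10% allowance.
- **Analysis.** The protocol text available mentions intention-to-treat and on-treatment analyses under Cross over. It mentions no covariate or subgroup for prior drug status. The SAP's text and part of the protocol had been removed before this review, so what they say about covariates is unknown.

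**The concern.** Prior drug failure is established for every patient before randomisation, because it is an entry criterion. The control arm gives drugs from the same list that failed patients have partly tried, so they start with fewer untried options. It is reasonable to expect lower drug-arm success in them, although the protocol gives no figure.

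Two things are at stake.

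- **Efficiency.** With about 83 patients per arm, the arms can differ by chance in their share of failures, and the estimated difference moves with that share. If the factor is prognostic, using it removes some avoidable noise.
- **Interpretation.** The protocol states one hypothesis for the whole population. If the effect differs between untreated and failed patients, the pooled result depends on the enrolled mix, and a reader cannot tell which group it describes unless both are shown.

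**Working it through.** **1. The plan's own figure.** Inputs from the Sample size section: 50% v 72%, power 0.8, alpha 0.05. Sidedness is not stated; two-sided with pooled variance and no continuity correction reproduces the plan.

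n = [1.96 x sqrt(2 x 0.61 x 0.39) + 0.842 x sqrt(0.25 + 0.2016)]^2 / 0.22^2 = 75.97, so 76 per arm, as stated. The total is 152 x 1.1 = 167.2, the stated 167.

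**2. Chance imbalance.** Assumption: half the patients are failures. Arms of 84 and 83, independent binomials.

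- SD of the between-arm difference in share = sqrt(2 x 0.25 / 83.5) = 0.077; 95% range +/-15 points.
- Exact P(|difference| > 10 points) = 0.216; P(> 15 points) = 0.049.
- Holding the overall share fixed, and counting differences of 10 points or more, gives 13-22% at N = 167 and 22-26% at N = 152, for shares of 30-70%.

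**3. Shift in the treatment difference.** Let d be the imbalance, and g_D and g_A the success gaps (untreated minus failed) on drugs and on ablation. With shares f + d/2 and f - d/2 in the two arms, the expected difference moves by d x (g_D + g_A)/2. The average of the two gaps matters, not the drug-arm gap alone. For a 15-point imbalance:

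| Assumed gap, drug / ablation | Average gap | Shift |
|---|---|---|
| 20 / 10 points | 15 | 0.15 x 15 = 2.3 points |
| 30 / 20 points | 25 | 0.15 x 25 = 3.8 points |

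The SD of the shift is 0.077 x 15 = 1.2 to 0.077 x 25 = 1.9 points. The standard error of the treatment difference is sqrt((0.25 + 0.2016)/83.5) = 7.4 points.

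**4. Power.** Simulation with 76 per arm, 50% share and at least 200,000 runs per scenario. It compares an unstratified, unadjusted z-test with stratified allocation plus the Cochran-Mantel-Haenszel (CMH) test. Where repeated runs differed, both values are shown.

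| Success untreated/failed: drug; ablation | Unstratified, unadjusted | Stratified + CMH | Gain |
|---|---|---|---|
| 60/40; 77/67 | 80.9-81.0% | 81.6% | about 0.6-0.7 |
| 65/35; 82/62 | 80.7-81.1% | 82.7-82.8% | about 1.7-2.0 |
| 60/40; 72/72 | 81.1-81.2% | 81.2% | about 0 |
| 65/35; 72/72 | 81.0-81.4% | 81.8-81.9% | about 0.5-0.7 |

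CMH without stratified allocation gave 80.8% in the first scenario and 82.6% in the second. Adjustment alone therefore gains nothing at the smaller gaps and most of the benefit at the larger ones. Stratified allocation adds under 1 point to it.

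**5. Type I error.** Under the null with a 20- or 30-point gap in both arms, the unstratified, unadjusted test rejects in 4.4% of runs. With stratified allocation, the unadjusted test falls to 4.1% and 3.5%, while CMH stays at 5.2% and 5.0%. Stratifying should therefore come with adjusting.

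**6. Dependence on the mix.** In the 60/40; 77/67 scenario the true effects are 77 - 60 = 17 points (untreated) and 67 - 40 = 27 points (failed). The pooled effect is 0.7 x 17 + 0.3 x 27 = 20 points at 30% failures and 0.3 x 17 + 0.7 x 27 = 24 points at 70%. With 38 per arm in each stratum, the 95% half-widths are 1.96 x sqrt((0.24 + 0.1771)/38) = 20.5 points and 1.96 x sqrt((0.24 + 0.2211)/38) = 21.6 points.

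**The case against.** The case for leaving the plan alone is substantial.

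- **The analysis may already handle it.** Covariates and subgroups belong in a SAP, and that text was not available. This stands: a reader might infer that the trial ignores the factor in its analysis, but the documents reviewed cannot show that. The point is confined to the protocol's randomisation text.
- **The factor's importance is assumed.** A reader might take prior drug failure to be the strongest determinant of drug-arm success. No passage says so. The factors the protocol does link to outcome are AF type, underlying disease and left atrial size. This stands; prior drug status is only a plausible prognostic factor.
- **Failed patients usually have an untried option.** Three first-level drugs and amiodarone are available, and those who have received them all are excluded. This may make the gap smaller than assumed here.
- **Chance imbalance is not bias.** The shift has an SD of 1.2-1.9 points against a standard error of 7.4, and ordinary confidence intervals already cover it. This stands. Inferring a biased comparison or an inflated type I error would be wrong.
- **One 50% rate for a mixed population is legitimate** as a marginal rate, and the protocol calls it a maximum. A reader might infer that the sample size is wrong; it is not. Nor does the hypothesis make a first-line claim, so a first-line misreading is a risk of reporting, not a defect in the plan.

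What remains is that a baseline status already determined at entry, and tied to the control regimen, is left out of the allocation text when including it costs almost nothing.

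**Conclusion.** The point holds as a minor, nearly free improvement. The protocol mixes drug-failed and untreated patients, and its randomisation section does not use that status. On an assumed 50% share of failures there is about a 22% chance of an imbalance above 10 points. On assumed success gaps of 20-30 points (drug) and 10-20 points (ablation), a 15-point imbalance shifts the result by about 2-4 points, and stratifying plus adjusting gains roughly 0.5-2 points of power. The gain is under 1 point, and about zero at the 20-point drug gap, if ablation success does not vary by stratum. The share and the gaps are assumptions that the documents neither give nor contradict. The planned 76 per arm is reproduced and need not change. Showing who the pooled result applies to is worth at least as much as the power.

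**What to change.** 1. Stratify the 1:1 randomisation by prior AAD status (failed / untreated), and state what counts as failed so that sites classify patients alike.
2. Unless the SAP already does so, estimate the primary effect with a Mantel-Haenszel risk difference stratified by this factor, or a model with it as a covariate. Do not stratify without adjusting.
3. Report the number enrolled and the treatment effect in each stratum, labelled descriptive because each estimate will be imprecise.
4. Say in the Sample size section that the 50% drug rate is meant for the mixed population, if that is the intention.

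If enrolment has begun, leave the allocation as it is and make only the adjustment and the stratum report.

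The cost is one stratification factor in the randomisation list, one covariate and one table. Prior status is already established at eligibility, and N does not change.

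### Does calling 72% the minimal cryoballoon success rate, when the Background quotes 69-77%, undermine the sample size?

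*Protocol*

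**What the plan says.** The Sample Size section of the protocol gives the two design rates: "The maximal expected 1 year success on AAD is 50% and minimal expected success of CBA is 72" per cent. It cites six references (3, 14, 15, 20, 21 and 22) without a derivation. With power 0.8 and significance 0.05 it arrives at approximately 76 patients per arm, and at 167 in total to allow for 10% not followed as required.

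The Background gives ranges for both treatments. For cryoballoon ablation (CBA), success was "reported after 1-year follow-up and later with a freedom from AF of 69-77% in patients using a cryoballoon technology (CBA"), citing references 12 to 14. For antiarrhythmic drugs (AAD), "most AAD have been shown only to be 40-50% effective in maintaining sinus rhythm".

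On the population, the Background says "Results are better in paroxysmal patients, than for persistent AF, also for CBA", and the Rationale says of early onset persistent AF without structural heart disease: "The value of CBA in these patients has never been studied". The same sections also argue the other way: "Differentiation between paroxysmal and short term persistent becomes almost impossible from a clinical point of view"; "persistent patients with normal left atrial dimensions made up an important proportion of our group"; and "Stop-AF only addressed paroxysmal patients (but included 22% cardioverted patients").

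The Endpoints section lists two primary endpoints: sinus rhythm at the one-year visit, and freedom from AF on all measurements. The Sample Size section does not say which of them the 72% describes.

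**The concern.** A maximal control rate paired with a minimal treatment rate reads as the smallest plausible difference. Power of 0.8 then looks like the least one should expect. Yet 72% lies inside the 69-77% of the Background, not at its lower end. The protocol also says that results are worse in persistent AF and that CBA has not been studied in this population. A minimum for an unstudied population would normally come with a stated basis.

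If the label is unsupported, so is the reassurance it carries. With AAD at 50%, any CBA rate below 72% puts power below 0.80, and the loss is steep: three percentage points cost about 13 points of power. A second, smaller doubt is that 167 does not quite cover a 10% loss.

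**Working it through.** **Inputs.** From Sample Size: AAD 0.50, CBA 0.72, power 0.80, significance 0.05, 76 per arm, 167 in total, 10% loss. From Randomization: 1:1. From Background: CBA 0.69 to 0.77, AAD 0.40 to 0.50. The AAD value of 0.45 used below is simply the midpoint of that range. The protocol does not state sidedness; two-sided is assumed because it reproduces the stated figure.

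**Reproducing 76 per arm.** Pooled two-proportion formula, no continuity correction:

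n = [1.960 × √(2·p̄·(1−p̄)) + 0.8416 × √(p₁(1−p₁) + p₂(1−p₂))]² / (p₂ − p₁)²

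With p₁ = 0.50, p₂ = 0.72 and p̄ = 0.61:

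- first term: 1.960 × √0.4758 = 1.352
- second term: 0.8416 × √0.4516 = 0.5656
- n = (1.352 + 0.5656)² / 0.0484 = 75.97, so 76 per arm

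The stated figure is reproduced.

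**Power at 76 per arm for other rates.**

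Power = Φ{ [(p₂ − p₁) − 1.960·√(2p̄(1−p̄)/76)] / √([p₁(1−p₁) + p₂(1−p₂)]/76) }

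Example, 50% versus 69%: p̄ = 0.595; 1.960 × √(0.48195/76) = 0.1561; √(0.4639/76) = 0.0781; (0.19 − 0.1561)/0.0781 = 0.434; Φ(0.434) = 0.668.

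| AAD | CBA 69% | CBA 72% | CBA 77% | CBA rate giving power 0.80 |
|---|---|---|---|---|
| 50% | 0.668 | 0.800 | 0.941 | 72.0% |
| 45% | 0.855 | 0.930 | 0.986 | 67.4% |
| 40% | 0.956 | 0.983 | 0.998 | 62.5% |

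Eight of the nine combinations reach 0.80. The one that does not pairs the unfavourable end of both ranges.

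**Are 69% and 72% the same quantity?**

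- *Time.* The 69-77% covers one year and later; the 72% is a one-year figure.
- *Sources.* The 69-77% cites references 12 to 14; the 72% cites six references, of which only reference 14 is shared.
- *Endpoint.* The 69-77% is freedom from AF. The first hypothesis names maintenance of sinus rhythm after one year, which is closer to the first primary endpoint. Leaving aside other non-sinus rhythms, a patient free of AF on every measurement is also in sinus rhythm at the visit. In a given cohort the sinus-rhythm rate should then be at least the freedom-from-AF rate. A 69% freedom from AF can therefore coexist with 72% in sinus rhythm.

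The 69% is thus a lower printed number, but not a demonstrated lower bound for the design quantity.

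**Loss to follow-up.**

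- 152 × 1.10 = 167.2, which explains the 167.
- Dividing by the retained fraction gives 152/0.90 = 168.9, so 169.
- Loss absorbed by 167: 15/167 = 9.0%.
- At 10% loss: 167 × 0.90 = 150.3, about 75 per arm; power for 50% versus 72% is then 0.795.

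The shortfall is two patients and about 0.005 of power.

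**The case for a change.** The strongest case for a change is that the label claims more than the protocol shows. The Background and the Sample Size section share reference 14, yet one prints 69-77% and the other a minimum of 72%, with nothing to connect them. A conservative AAD rate does not make the CBA rate a minimum. The drop from 0.80 to 0.67 for a three-point shift cannot be seen from the paragraph. Replacing the two adjectives with a neutral word and adding a short sensitivity table would be cheap.

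Part of this stands. 72% is not the lowest CBA figure the protocol quotes, its derivation and endpoint are not given, and 0.8 should not be read as a guaranteed minimum. But the protocol never calls 0.8 a floor; that reading is an inference. Power falls below target whenever the true effect is smaller than the design effect, in any trial.

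The persistent-AF argument is also two-sided. The protocol says early persistent and paroxysmal AF are hard to separate clinically, and it restricts entry by left atrial size and structural disease.

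The proposed table has its own weakness. It crosses an AAD range for maintaining sinus rhythm with a CBA range for freedom from AF, so it is not strictly the power for either primary endpoint. It also ignores dilution of the intention-to-treat comparison by the cross-over allowed after six months, for which the protocol gives no rate.

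**Conclusion.** The concern does not call for a change. The calculation is right, and what remains is an adjective without a stated justification. The documents do not show 72% to be wrong for one-year success, and they do not establish 69% as the true minimum. The control rate was taken at the unfavourable end of its range, which offsets optimism about CBA: with AAD at 45%, a CBA rate of 69% still gives power 0.86. The figure of 0.67 at 50% versus 69% is one corner of the protocol's own figures and should not be presented as the expected or the worst case.

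The loss allowance is a clerical slip in the inflation step. Power of 0.795 is still 0.8 at the precision stated, and 75 per arm fits a target given as approximate.

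Relabelling both rates as assumptions would read better, but it would change no sample size, endpoint, analysis or conclusion. This rests on a two-sided pooled test, on the Background ranges as printed, and on no adjustment for cross-over. Whether the cited sources support 72% as a minimum cannot be judged from the protocol.
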